4.4 Retention Strategies

Retention of subjects is not applicable since study procedures will be completed in a single visit.

4.5 Study Procedures

Primary Objective

To determine whether liver stiffness as assessed by shear wave elastography (SWE) is higher in individuals with ASS1D, ASLD and ARG1D as compared to females with OTCD and to assess liver stiffness in other UCDs (citrin deficiency, NAGSD, CPS1D, and males with OTCD),

Secondary Objective

To test whether markers of hepatocellular injury and function and novel serum biomarker panels for hepatic fibrosis provide evidence of chronic liver disease in individuals with ASS1D, ASLD and ARG1D as compared to OTCD, and to assess these sample markers

of hepatocellular injury and function and novel serum biomarker panels for hepatic fibrosis in other UCDs (citrin deficiency, NAGSD, CPS1D, and males with OTCD).

Study Procedures

This study will entail a single visit to the UCDC site. Subjects will come to the hospital or research center to sign the informed consent prior to conducting any procedures.

Subjects will be asked to not eat or drink for at least four hours prior to arrival for the study visit. Vital signs including height, weight, heart rate, blood pressure, respiration rate and temperature will be measured. A blood sample of approximately 4 teaspoons or 20 mL will be collected to assess complete blood count (CBC), blood ammonia, aspartate aminotransferase (AST), alanine aminotransferase (ALT), gamma glutamyl transferase (GGT), total bilirubin, conjugated bilirubin, albumin, Prothrombin time (PT), Internationalized Normalized Ratio (INR), AST-to-Platelet Ratio (APRI), and Fibrotest. These tests will be ordered individually or as part of a panel test (e.g., hepatic function panel) if such a panel is available at the study site. A storage sample for future biochemical studies will also be collected. A urine sample for pregnancy testing will be collected if a female is of childbearing age.

If anything clinically significant were to be found on the ultrasound or the blood work, it will be reported to the subject and their clinical care provider.

A medical history will be reviewed and recorded. We will collect information from medical records including results from the most recent test and reports from a previous liver biopsy results if it is available.

A single ultrasound exam that includes shear-wave elastography (SWE) will be used to measure liver stiffness. A radiology technician or radiologist will perform the exam. The study should be completed in one outpatient visit. However, based on patient preferences, the ultrasound and blood draw may have to be schedules on two separate days. In such circumstances, both the blood draw and the ultrasound will be performed within a time period of two weeks.

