| Study Population and Main Eligibility/ Exclusion Criteria: | 
Inclusion Criteria
 
 1. Age \geq 5 years and \leq 60 years 2. Weight \geq 11 kg 3. Males or females with a diagnosis of OTCD based on molecular or enzymatic testing. Males or females with a diagnosis of CPS1D, citrin deficiency, NAGSD, ASS1D, ASLD or ARG1D based on biochemical OR molecular, OR enzymatic testing 
Exclusion Criteria
 
 1. History of hyperammonemia (blood ammonia greater than 100 micromoles/L) documented in the medical record or reported by the patient in the 30 days preceding enrollment visit 2. History of Liver transplantation 3. Current pregnancy 4. Confirmed diagnosis of chronic viral hepatitis, autoimmune liver disease, or alcohol liver disease |
| Primary Outcome Measures: | Z-scores for liver stiffness as measured by 
 • shear wave velocity in m/s • elasticity in kPa |
| Secondary Outcome Measures: | Plasma levels of 
 • Aspartate transaminase • Alanine transaminase |

| | |

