| Statistical Considerations (sample size and analysis plan): | 
This is a cross-sectional pilot study. The mean shear wave velocity and elasticity and the mean values of serum biomarkers will be compared among the individual disorders (ASS1D, ARG1D, ASLD) and OTCD using a one-way ANOVA. Any correlation between the shear wave velocity and serum markers will be assessed by using appropriate correlation statistical methods. For the other disorders (CPS1D, NAGSD, citrin deficiency, and males with OTCD males,) we expect that sample size will be limited given that these disorders are ultra-rare or given that many patients receive early liver transplantation as part of routine management. Thus, data analysis for these other disorders will be descriptive only.
 
Published data demonstrate that the mean (SD) shear wave velocities in population without liver disease to be 1.56 (0.4) m/s. We would expect that individuals with OTCD would have values comparable to these values. In individuals with ASLD and ARG1D, we would expect higher shear wave velocities comparable to individuals with grade 2-3 liver fibrosis. The mean shear wave velocities (SD) grade 3 fibrosis is 2.57 m/s (0.3). We hypothesize that the mean shear wave velocity in ASS1D will be intermediate between ASLD/ARG1D and controls. Assuming a normal distribution for, with a sample size of 8 individuals per group, we will be able to detect a minimum difference in means of 0.79 m/s, when the standard deviation is 0.4 m/s, at an alpha error of 0.05 and a power of 0.8.
 |
| Sponsors (federal, state, foundation and industry support): | National Institutes of Health (NIH) |

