The purpose of this study is: 1) To determine whether liver stiffness is higher in individuals with ASS1D, ASLD, and ARG1D as compared to females with OTCD, and to assess liver stiffness in other UCDs (citrin deficiency, NAGSD, CPS1D, and males with OTCD), 2) To test whether markers of hepatocellular injury and function and novel serum biomarker panels for hepatic fibrosis provide evidence of chronic liver disease in individuals with ASS1D, ASLD, and ARG1D as compared to OTCD and to assess these sample markers of hepatocellular injury and function and novel serum biomarker panels for hepatic fibrosis in other UCDs (citrin deficiency, NAGSD, CPS1D, and males with OTCD).

2. Specific Aims (Hypothesis and Objectives)

Hypothesis:

We hypothesize that individuals with ASLD and ARG1D will have higher liver stiffness as assessed by non-invasive ultrasonographic techniques and greater serum biomarker evidence for fibrosis as compared to females with OTCD. We hypothesize that individuals with ASS1D will have liver stiffness and serum biomarkers that are intermediate between OTCD and the other two distal disorders (ASLD and ARG1D).

Study Objectives:

Specific Aim #1: To determine whether liver stiffness is higher in individuals with ASS1D, ASLD, and ARG1D as compared to females with OTCD, and to assess liver stiffness in other UCDs (citrin deficiency, NAGSD, CPS1D, and males with OTCD),

Specific Aim #2: To test whether markers of hepatocellular injury and function and novel serum biomarker panels for hepatic fibrosis provide evidence of chronic liver disease in individuals with ASS1D, ASLD, and ARG1D as compared to OTCD and to assess these sample markers of hepatocellular injury and function and novel serum biomarker panels for hepatic fibrosis in other UCDs (citrin deficiency, NAGSD, CPS1D, and males with OTCD).

We will conduct a pilot, cross-sectional study to assess liver stiffness and markers of hepatic injury, function, and fibrosis in patients with ASLD, ARG1D, ASS1D, and OTCD and in patients with other UCDs (citrin deficiency, NAGSD, CPS1D, and males with OTCD). This study will be conducted at 3 UCDC sites: Baylor College of Medicine in Houston, Texas, University of California San Francisco (UCSF), San Francisco, California and Seattle Children's Hospital, Seattle, Washington.

3. Background

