4.6 Data Elements

Once referred for screening, the participant's diagnostic testing will be reviewed to assure that the eligibility requirements are met based on study inclusion and exclusion criteria. Data will be collected at a single study visit per the Schedule of Events. We will use a variety of methods to obtain these data. Certain information will be obtained from a historical review of existing medical records including laboratory and treatment data. Other data will be obtained from patients or their families through a standard interview, examination or laboratory/functional testing.

The study will maintain appropriate medical and research records. As part of conducting the study, sites will maintain all relevant source data. Source data are all information and original records of clinical findings, observations, or other activities necessary for the study. Examples of original source documentation include original documents and data records, electronic medical records, laboratory reports, memoranda, recorded data from automated instruments, copies and transcriptions after the copy has been verified as being accurate and complete, photographic negatives, x-rays, etc.

Shear Wave Elastography will be performed by experienced radiology personnel using standard equipment and protocols. The laboratory assessments will be performed in CLIA-certified laboratories or the research laboratory facilities at Baylor College of Medicine.

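### The protocol does not say that the elastography operator is kept unaware of the disorder, laboratory results or biopsy history, although the primary outcome is one operator-acquired exam and the hypothesis is directional by disorder

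*Protocol*

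**What the plan says.** The Protocol Synopsis defines the primary outcome as "Z-scores for liver stiffness as measured by" shear wave velocity (m/s) and elasticity (kPa). Section 4.5 provides for one measurement occasion: "A single ultrasound exam that includes shear-wave elastography (SWE) will be used to measure liver stiffness".

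Two sentences set conditions on the operator. Section 4.5: "A radiology technician or radiologist will perform the exam". Section 4.6: "Shear Wave Elastography will be performed by experienced radiology personnel using standard equipment and protocols".

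The expected result is stated by disorder. Section 2 hypothesises that "individuals with ASLD and ARG1D will have higher liver stiffness as assessed by non-invasive ultrasonographic techniques", the comparator being females with OTCD. The Synopsis, under Statistical Considerations, adds: "We hypothesize that the mean shear wave velocity in ASS1D will be intermediate between ASLD/ARG1D and controls". The same entry plans a one-way ANOVA across ASS1D, ARG1D, ASLD and OTCD, and a correlation of velocity with serum markers.

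Section 4.5 also has the study collect recent test results and any earlier biopsy report from medical records. It allows the blood draw and the ultrasound to fall on separate days within two weeks if the patient prefers, without fixing their order. Neither document mentions masking, a second reader, central reading or a repeat exam.

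**The concern.** The groups are defined by diagnosis, so randomisation cannot separate knowledge of group from the measurement. The primary value comes from a person performing a single exam, and the protocol says in advance which disorders should read high, intermediate and normal. An operator who knows the disorder and shares that expectation could produce readings that lean the predicted way. No later measurement would reveal it.

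Two analyses are exposed. The by-disorder comparison in Aim 1 could show a difference that is partly or wholly expectation. Where blood is drawn on an earlier day and the results reach the operator, the velocity-marker correlation could also be affected.

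**Working it through.** **1. What the documents settle.** Sections 4.5 and 4.6 name the type of operator, the experience, and the use of standard equipment and protocols. Section 3 adds that elastography has excellent intra- and interobserver reproducibility. All of these bear on random error and on agreement between operators. None bears on a shift common to operators who know the diagnosis, since such operators can agree closely and still be displaced together. Masking is therefore unspecified, and nothing else in the plan does its work.

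**2. The plan's own figure.** The Synopsis states a detectable difference of 0.79 m/s with n = 8 per group, SD 0.4, alpha 0.05 and power 0.8. For a two-sample t-test the standard error is 0.4 × √(2/8) = 0.2 m/s, with 14 degrees of freedom.
- Two-sided, unadjusted alpha 0.05: detectable difference 0.60 m/s; power at 0.79 is 95.6%.
- Two-sided, alpha 0.05/6 (Bonferroni over the six pairs of four groups): detectable difference 0.797 m/s; power at 0.79 is 79.2%.

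The stated figure is reproduced by the second variant, although the protocol does not state that adjustment. This confirms n and SD as inputs for the next step.

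**3. Effect of an assumed shift when there is no true difference.** Assume expectation adds b to the mean in ASLD and ARG1D, b/2 in ASS1D and nothing in OTCD. The documents give no value for b, so 0.1, 0.2 and 0.3 m/s are used. These are 0.25, 0.5 and 0.75 SD, or about 10%, 20% and 30% of the planned gap of 2.57 − 1.56 = 1.01 m/s.

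*Planned four-group ANOVA.* The group means are 0, b/2, b, b and their average is 0.625b. The sum of squared deviations is (0.390625 + 0.015625 + 0.140625 + 0.140625)b² = 0.6875b². The noncentrality is 8 × 0.6875b² / 0.4² = 34.375b², with 3 and 28 degrees of freedom and critical F 2.947.

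*One unadjusted two-sided t-test of ASLD or ARG1D against OTCD.* The noncentrality is b/0.2, with 14 degrees of freedom and critical t 2.145.

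*The same t-test at 0.05/6.* Critical t is 3.069.

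| b (m/s) | ANOVA noncentrality | ANOVA, P<0.05 | t noncentrality | t-test, P<0.05 | t-test at 0.05/6 |
|---|---|---|---|---|---|
| 0 | 0 | 5% | 0 | 5% | 0.8% |
| 0.1 | 0.344 | 6.8% | 0.5 | 7.5% | 1.5% |
| 0.2 | 1.375 | 13.0% | 1.0 | 15.4% | 4.0% |
| 0.3 | 3.094 | 24.9% | 1.5 | 28.7% | 9.4% |

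**4. Effect when the planned difference is real.** With a true gap of 1.01 m/s, power is 99.7% for the unadjusted t-test. It is 99.8% for the ANOVA with ASS1D halfway (1.56, 2.065, 2.57, 2.57). A shift then hardly changes whether the test is significant. It adds to the estimated difference: 0.2 m/s would turn 1.01 into 1.21.

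**5. The correlation.** The documents give no basis for sizing an effect on the velocity-marker correlation. It needs three things: blood drawn before the scan, results available, and results seen by the operator. The protocol rules none of these out and establishes none of them.

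**The case against.** The strongest objection is that the documents are silent. A reader might infer that operators are told the diagnosis, but no sentence says so. The collection of records and biopsy reports in 4.5 describes study data, not what reaches radiology, and section 4.3 gives recruitment to physicians, nurses and coordinators. Bias needs an operator who knows both the disorder and what is expected of it. This stands: the point is a missing safeguard, not a demonstrated bias.

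Three other inferences are tempting and unsupported.
- That each participant is scanned at their own metabolic centre: section 4.3 also recruits through a contact registry, the patient foundation and nationwide consultation.
- That the operator chooses where to measure and which readings to keep: the protocol does not describe region, number of readings or rejection rules, and 4.6 points to standard protocols.
- That masking the operator is the only protection: standardised acquisition and masked review of stored images would each help in part.

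The size is also assumed. A shift of 0.3 m/s is 0.75 SD, and it would have to be shared across three sites and line up with disorder. The ANOVA figures are lower than those of the unadjusted t-test, and at the 0.05/6 level the rates are lower still. At 0.1 m/s the inflation is slight.

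Finally, this is a pilot in very rare disorders, and the SAP, dated May 2022, is written in the past tense, so scanning may be finished. That limits what can still be changed. It does not make the comparison safe from a shift tied to known diagnosis.

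**Conclusion.** The concern holds as an omission. The protocol does not specify that the elastography operator is unaware of the disorder, laboratory results or biopsy history, in a non-randomised comparison that rests on one operator-acquired exam and a directional hypothesis. If operators know the disorder, expectation could shift the Aim 1 contrast.

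Under the assumed shifts and no true difference, the planned ANOVA's false-positive rate rises from 5% to about 7%, 13% or 25% (8%, 15% or 29% for one unadjusted t-test). The effect is minor at 0.1 m/s and material from about 0.2 m/s. If the planned gap is real, the consequence is a distorted estimate rather than a false finding. These figures rest on n = 8 per group, SD 0.4 m/s, a shift halved in ASS1D, and a shift size that the documents do not supply. The change is worth making because it is cheap, not because bias has been shown.

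**What to change.** Add to section 4.5:
- The elastography request carries only the study ID and the label 'urea cycle disorder study'.
- The disorder, laboratory results and any earlier biopsy report are withheld from the operator until the velocity and kPa readings are saved. They can be released straight afterwards, so the existing reporting of clinically significant findings is unaffected.
- The operator records whether the disorder was known at the time of the scan.

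In the analysis, report the number of unmasked scans per group. Show the by-disorder comparison excluding them as descriptive only, because groups of 8 may leave very few scans.

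The cost is a revised request form and one tick box on the case report form, with no extra scan, reader or staff. The downside is incomplete masking where staff know the patient, the patient mentions the diagnosis, or the chart is open. For scans already done, document what operators knew and report it as a limitation.

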4.6 Data Elements

Once referred for screening, the participant's diagnostic testing will be reviewed to assure that the eligibility requirements are met based on study inclusion and exclusion criteria. Data will be collected at a single study visit per the Schedule of Events. We will use a variety of methods to obtain these data. Certain information will be obtained from a historical review of existing medical records including laboratory and treatment data. Other data will be obtained from patients or their families through a standard interview, examination or laboratory/functional testing.

The study will maintain appropriate medical and research records. As part of conducting the study, sites will maintain all relevant source data. Source data are all information and original records of clinical findings, observations, or other activities necessary for the study. Examples of original source documentation include original documents and data records, electronic medical records, laboratory reports, memoranda, recorded data from automated instruments, copies and transcriptions after the copy has been verified as being accurate and complete, photographic negatives, x-rays, etc.

Shear Wave Elastography will be performed by experienced radiology personnel using standard equipment and protocols. The laboratory assessments will be performed in CLIA-certified laboratories or the research laboratory facilities at Baylor College of Medicine.

4.7 Schedule of Events

| | |
|---------------------------------------------------------------------------------------------------------------------------------------------------------------------------------------------------------------------------------------------------------------------------------------------------------------------------|---|
| Sign Informed Consent | X |
| Confirm eligibility | X |
| Vital Signs: Blood pressure, temperature, heart rate, respirations measured | X |
| Blood draw for complete blood count (CBC), blood ammonia, aspartate aminotransferase (AST), alanine aminotransferase (ALT), albumin, gamma glutamyltransferase (GGT), total bilirubin, conjugated bilirubin, Prothrombin time (PT), Internationalized Normalized Ratio (INR), AST-to-Platelet Ratio (APRI), and Fibrotest | X |
| Urine pregnancy test for females of child bearing Age | X |
| Review medical history | X |
| Ultrasound SWE imaging | X |

Chronic Liver Disease in Urea Cycle Disorders

ClinicalTrials.gov Identifier: NCT03721367

5-11-2022

Demographic characteristics, medical history, and liver biomarkers were summarized using means and standard deviations for continuous outcomes and counts and frequencies for categorical outcomes. For each outcome, we stratified subject characteristics summaries by normal or abnormal readings. For the strength of association between outcome measures and subject characteristics, univariate analyses were used (independent t-test for comparison of means and chi-square test for comparison of proportions). $P < 0.05$ (nominal) was considered as statistically significant. All statistical analyses were conducted using R or Graphpad Prism v.8.4.2 software (San Diego, CA).

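### The SAP omits, without explanation, the protocol's four-group ANOVA of stiffness and biomarkers and its stiffness-biomarker correlation, so as written it does not test the primary objective

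*SAP*

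**What the plan says.** **Protocol, section 1 (Synopsis, Statistical Considerations).** The planned comparison is by disorder and on means: "The mean shear wave velocity and elasticity and the mean values of serum biomarkers will be compared among the individual disorders", with OTCD as the fourth group and a one-way ANOVA as the method. A second analysis follows: "Any correlation between the shear wave velocity and serum markers will be assessed by using appropriate correlation statistical methods". For CPS1D, NAGSD, citrin deficiency and OTCD males, "data analysis for these other disorders will be descriptive only". Sample size is argued from means: with 8 per group, SD 0.4 m/s, alpha 0.05 and power 0.8, "we will be able to detect a minimum difference in means of 0.79 m/s".

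**Protocol, sections 2, 4.3 and 4.5.** The primary objective asks whether stiffness is higher in ASS1D, ASLD and ARG1D than in female OTCD patients. Section 4.3 plans 8 OTCD females. The ANOVA sentence itself says only OTCD. That the comparison group is female follows from these sections and from OTCD males being descriptive only. Section 2 also hypothesises that ASS1D lies between OTCD and the ASLD/ARG1D pair.

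**SAP (one paragraph, dated 5-11-2022, past tense).** After descriptive summaries it says: "For each outcome, we stratified subject characteristics summaries by normal or abnormal readings". Associations between outcomes and subject characteristics were tested by "independent t-test for comparison of means and chi-square test for comparison of proportions", with nominal P < 0.05 taken as significant.

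**The concern.** The SAP names no ANOVA, no disorder group, no OTCD reference and no correlation. Its only stated grouping is normal against abnormal readings, for which it gives no cut-off. That asks a different question: how people with abnormal readings differ from people with normal ones, not whether one disorder has stiffer livers than another.

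The stake is the primary objective. The recruitment targets, the 8 per group and the hypotheses are all built on comparing mean stiffness between disorders. Someone following the SAP alone would produce no stated test or estimate of that comparison, and no biomarker ANOVA or correlation. A reader of the results could not tell planned analyses from those chosen later.

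**Working it through.** **1. The two documents side by side.**

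| Element | Protocol | SAP |
|---|---|---|
| Grouping | Four disorder groups | Normal or abnormal reading |
| Test of means | One-way ANOVA | Independent t-test |
| Serum biomarkers | ANOVA by disorder | Summaries; t-test or chi-square |
| Velocity with serum markers | Correlation, method not named | None |
| Reason for a difference | - | None given |

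**2. Could the SAP's tests stand in?** Subject characteristics are not defined and might include diagnosis. An independent t-test compares two groups, so it is not a four-group comparison of means. A chi-square test compares proportions, so it compares no means at all. Neither correlates two continuous measures. The omission therefore stands on either reading.

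**3. The protocol's own sample-size figure.** Inputs from the synopsis: n = 8 per group, SD 0.4, alpha 0.05, power 0.8.
- Two-sided two-sample t-test, noncentrality (d/0.4) × √(8/2): detectable difference 0.603 m/s.
- Four-group ANOVA, λ = 8 × Σ(mean − grand mean)²/0.4², least favourable means: 0.708 m/s. At a range of 0.79 (means 1.56, 1.955, 1.955, 2.35), λ = 8 × (2 × 0.395²)/0.16 = 15.6 and power is 88.5%.
- Two-sided t-tests, Bonferroni over all six pairs of four groups: 0.797 m/s, with power 79.2% at 0.79.

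The stated 0.79 m/s is matched by the six-pair version, an adjustment the protocol does not mention, and is conservative for the ANOVA. On every version the sample size concerns differences in means between disorder groups, which is the analysis the SAP leaves out.

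**4. Error rate if diagnosis enters through pairwise t-tests.** Four groups give 4 × 3/2 = 6 pairs, of which 3 are against OTCD. If the tests were independent, the chance of at least one false positive would be 1 − 0.95⁶ = 26.5% for six and 1 − 0.95³ = 14.3% for three. The tests share groups, so the true figures are lower. Simulating 200,000 null trials of four groups of 8 gives 20.3% for six and 12.6% for three, on one stiffness measure. The protocol has two stiffness measures, so the chance over both is higher, by an amount that depends on a correlation the documents do not give.

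**5. Cost of adjusted intervals.** The half-width of a difference is c × 0.4 × √(1/8 + 1/8) = c × 0.2, with the SD pooled on 28 df. Unadjusted, c = 2.05 gives 0.41 m/s. Dunnett for three comparisons with OTCD, c = 2.48 (simulated), gives 0.50 m/s. If ASS1D lies midway between 1.56 and 2.57 m/s, its difference from OTCD is 1.01/2 = 0.505 m/s. Power for that is about 65% with a separate unadjusted t-test and about 52% with Dunnett.

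**The case against.** The best defence is that silence is not replacement. The protocol still states the ANOVA and the correlation, both documents are public, and the SAP reads like a short methods summary of a self-described pilot. On that view it need not repeat the protocol, and the sponsor need only say whether the planned analyses were done.

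Part of this stands. The SAP does not revoke the protocol's plan. A reader might infer that the ANOVA was abandoned, or that the normal/abnormal grouping was chosen after seeing the data. Neither document shows that. But the SAP sets out the inferential tests used and which software ran all the analyses, and from it nobody can tell whether the primary comparison was made. The pilot label does not excuse this either: the same synopsis uses it and still specifies an ANOVA, an alpha and a power, reserving descriptive analysis for the other disorders.

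A reader might also infer a large loss of power from splitting stiffness into normal and abnormal. The documents do not support a figure, because no cut-off is stated. With cut-offs assumed at 1 to 2.33 SD above the OTCD mean, an 8 v 8 chi-square test has anywhere from 90% to 30% power at 0.79 m/s (96% for the t-test), and at 1.01 m/s the loss is small for most of those cut-offs.

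Nor do the documents show that groups fell short. The lowest site projections in Table 1 sum to 5 or 6 per group, but the highest sum to 9 to 11 and the target is 8.

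**Conclusion.** The point holds and must be fixed. The SAP omits both inferential analyses planned in the protocol and gives no reason, and followed as written it does not deliver the test of the primary objective. This rests on the text alone and is held with high confidence. The only size attached is conditional: if diagnosis was examined by unadjusted pairwise t-tests, the false-positive chance on one measure is about 20% for six tests or about 12.5% for three, assuming 8 per group, normal data and equal SDs.

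What was actually run remains unknown, and no power loss is claimed.

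A separate, minor matter is that the synopsis names Z-scores as the primary outcome while its analysis text uses raw means, and no Z-score reference standard is stated. A reader might take this as a further defect in the test. Under a single fixed reference, however, a Z-score is a linear rescaling and leaves F and P unchanged. It should be reconciled on its own account.

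**What to change.** In the SAP:

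- State the protocol's one-way ANOVA of shear wave velocity and of elasticity across female OTCD, ASS1D, ASLD and ARG1D as the primary analysis.
- State the ANOVA of serum biomarkers and the correlation of velocity with serum markers as secondary, and name the correlation method.
- Report ASS1D, ASLD and ARG1D each minus female OTCD with a 95% CI. Report ASS1D against ASLD and against ARG1D as well, because contrasts with OTCD alone cannot address the intermediate hypothesis.
- Label these contrasts, and any multiplicity adjustment, as added after the protocol. Dunnett is one option for the three comparisons with OTCD; it does not cover the other two.
- Label the normal/abnormal tables and tests exploratory and give the cut-offs.
- Keep CPS1D, NAGSD, citrin deficiency and OTCD males descriptive.
- Say whether the protocol's analyses were done, and explain any departure.

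The cost is SAP wording, a disclosure sentence and a short analysis. No new subjects or procedures are needed if the data are in hand, as the SAP's past tense suggests. Adjustment would widen the intervals and lower power for the ASS1D contrast, as worked out above. If the ANOVA has already been done, saying so and reporting it meets most of the request.
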